7.6 Visit 3 (Study Week 1 +2 days)

The following tests and evaluations will be performed:

- Review medical history for events since last visit;
- Review concomitant meds since last visit;
- Review voiding diaries;
- Participants complete global assessment of disease state and response to treatment;
- Physical examination including urogenital examination and vital signs
- Electrocardiogram;
- Obtain blood for the following laboratory determinations:
 - Hematology: Complete Blood Count (CBC) with differential, platelet count, sedimentation rate (sed rate), PT and PTT.
 - Fasting chemistry: Blood Urea Nitrogen (BUN), creatinine, electrolytes (Na⁺, K⁺, Ca⁺⁺, Mg⁺⁺, CO₂, Cl), albumin, alkaline phosphatase, ALT, AST, GGT, LDH, CPK, total bilirubin, total protein, C-reactive protein (CRP), antinuclear antibody (ANA), and glucose;
- Obtain urine for routine urine analysis: microscopic RBC and WBC, protein, glucose, nitrites, and specific gravity, pH;
- Collect and weigh pads used for 72 hours;
- Obtain urine and blood specimen for analysis of *hSlo* cDNA with PCR;
- Obtain urine culture by clean void;

- Provide patient with diary materials;
- Instruct the participant to complete daily voiding diaries for 7 days prior to next visit and return with results at next visit including pads used for 72 hours prior to that visit (and clean pad to be used as a baseline). The site must call participants at least 7-8 days prior to next scheduled visit to remind patient to complete the diaries for 7 days prior to next visit;

7.7 Visit 4 (Study Week 2 +2 days)

Two weeks after administration of study drug the participant will return to the clinic. The following tests and evaluations will be performed on the participants:

- Review medical history for events since last visit;
- Review concomitant meds since last visit;
- Review voiding diaries
- Collect and weigh pads used for 72 hours
- Participants complete global assessment of disease state and response to treatment;
- Physical examination including urogenital examination and vital signs
- Bladder scan for residual volume and bladder capacity (prior to catheterization);
- Blood specimens for the following laboratory determinations:
 - Hematology: Complete Blood Count (CBC) with differential, platelet count, sedimentation rate (sed rate).
 - Fasting chemistry: Blood Urea Nitrogen (BUN), creatinine, electrolytes (Na⁺, K⁺), C-reactive protein (CRP), glucose, and ANA.
- Obtain urine for routine urine analysis: microscopic RBC and WBC, protein, glucose, nitrites, pH, and specific gravity;
- Obtain urine and blood specimen for analysis of *hSlo* cDNA with PCR;
- Provide patient with diary materials;
- Instruct the participant to complete daily voiding diaries and return with results at next visit including pads used for 72 hours prior to that visit (and clean pad to be used as a baseline) The site must call participants at least 7-8 days prior to next scheduled visit to remind patient to complete the diaries for 7 days prior to next visit;

7.8 Visit 5 (Study Week 4)

The following tests and evaluations will be performed:

- Review medical history for events since last visit;
- Review concomitant meds since last visit;

- Review voiding diaries;
- Collect and weigh pads used for 72 hours
- Participants complete KHQ and SF-12 (QoL), global assessment of disease state, and response to treatment prior to cystometry;
- Participants complete ICIQ-SF prior to cystometry;
- Physical examination including urogenital examination and vital signs prior to cystometry
- Blood specimens for the following laboratory determinations prior to cystometry:
 - Hematology: Complete Blood Count (CBC) with differential, platelet count, sedimentation rate (sed rate), PT and PTT.
 - Fasting chemistry: Blood Urea Nitrogen (BUN), creatinine, electrolytes (Na⁺, K⁺, Ca⁺⁺, Mg⁺⁺, CO₂, Cl), albumin, alkaline phosphatase, ALT, AST, GGT, LDH, total bilirubin, total protein, C-reactive protein (CRP), CPK, antinuclear antibody (ANA), and glucose.
 - Urine analysis: microscopic RBC and WBC, protein, glucose, nitrites, pH, and specific gravity;
- Electrocardiogram prior to cystometry;
- Collect urine for culture **prior to cystometry** using urodynamic catheter
- Obtain urine and blood specimen for analysis of *hSlo* cDNA with PCR prior to cystometry;
- Perform cystometry;
- Collect first voided urine (clean void) for culture prior to discharge;
- Provide patient with diary materials;
- Instruct the participant to complete daily voiding diaries and return with results at next visit including pads used for 72 hours prior to that visit (and clean pad to be used as a baseline). The site must call participants at least 7-8 days prior to next scheduled visit to remind patient to complete the diaries for 7 days prior to next visit;

7.9 Visit 6 (Study Week 8)

The following tests and evaluations will be performed:

- Review medical history for events since last visit;
- Review concomitant meds since last visit;
- Review voiding diaries;
- Collect and weigh pads used for 72 hours
- Participants complete KHQ and SF-12 (QoL), global assessment of disease state and response to treatment;

- Participants complete ICIQ-SF;
- Physical examination including urogenital examination and vital signs;
- Obtain urine and blood specimen for analysis of *hSlo* cDNA with PCR;
- Bladder scan for residual volume and bladder capacity;
- Provide patient with diary materials;
- Instruct the participant to complete daily voiding diaries and return with results at next visit including pads used for 72 hours prior to that visit (and clean pad to be used as a baseline). The site must call participants at least 7-8 days prior to next scheduled visit to remind patient to complete the diaries for 7 days prior to next visit;

7.10 Visit 7 (Study Week 12)

The following tests and evaluations will be performed:

- Review medical history for events since last visit;
- Review concomitant meds since last visit;
- Review voiding diaries;
- Participants complete KHQ and SF-12 (QoL), global assessment of disease state and response to treatment;
- Participants complete ICIQ-SF;
- Physical examination including urogenital examination and vital signs;
- Obtain urine and blood specimens for analysis of *hSlo* cDNA with PCR;
- Obtain blood for the following laboratory determinations:
 - Hematology: Complete Blood Count (CBC) with differential, platelet count, sedimentation rate (sed rate), PTT and PT.
 - Fasting chemistry: Blood Urea Nitrogen (BUN), creatinine, electrolytes (Na⁺, K⁺, Ca⁺⁺, Mg⁺⁺, CO₂, Cl), albumin, alkaline phosphatase, ALT, AST, GGT, LDH, total bilirubin, total protein, C-reactive protein (CRP), CPK, antinuclear antibody (ANA), and glucose.
- Obtain urine for routine urine analysis: microscopic RBC and WBC, protein, glucose, nitrites, pH, and specific gravity;
- Collect and weigh pads used for 72 hours;
- Provide patient with diary materials;
- Instruct the participant to complete daily voiding diaries and return with results at next visit including pads used for 72 hours prior to that visit (and clean pad to be used as a baseline). The site must call participants at least 7-8 days prior to next scheduled visit to remind patient to complete the diaries for 7 days prior to next visit.

7.11 Visit 8 (Study Week 24) or Exit Visit:

The following tests and evaluations will be performed:

- Review medical history for events since last visit;
- Review concomitant meds since last visit;
- Review voiding diaries;
- Participants complete KHQ and SF-12 (QoL), global assessment of disease state and response to treatment;
- Participants complete ICIQ-SF;
- Physical examination including urogenital examination and vital signs (and weight);
- Electrocardiogram;
- Bladder scan for residual volume and bladder capacity (prior to catheterization);
- Perform cystometry;
- Obtain blood for the following laboratory determinations:
 - Hematology: Complete Blood Count (CBC) with differential, platelet count, sedimentation rate (sed rate), PTT and PT.
 - Fasting chemistry: Blood Urea Nitrogen (BUN), creatinine, electrolytes (Na⁺, K⁺, Ca⁺⁺, Mg⁺⁺, CO₂, Cl), albumin, alkaline phosphatase, ALT, AST, GGT, LDH, CPK, total bilirubin, total protein, C-reactive protein (CRP), antinuclear antibody (ANA), and glucose.
- Urine analysis: microscopic RBC and WBC, protein, glucose, nitrites, pH, and specific gravity (prior to ultrasound and cystometry);
- Collect and weigh pads used for 72 hours
- Collect urine for culture prior to cystometry procedures using urodynamic catheter;
- Collect first clean voided urine for culture prior to discharge after cystometry;
- Obtain urine and blood specimens for analysis of *hSlo* cDNA. If DSMB informs the site that *hSlo* was detectable in either of two preceding specimens, participants will be required to return monthly to the clinic post study until there are two negative specimens.

7.12 Visit schedule and Visit Windows

In this outpatient study, every attempt must be made to adhere to the structured visit schedule. The Screening period (Visit 1 and 1A) should not exceed 14 days (± 2 days) unless approved by Sponsor or designee (e.g., UTI found during Screening). All other visits should occur with respect to previous visit: V2, at least 8 days after V1A + 2 days; V3 +2 days; V4 +2 days; V5 ± 2 days; V6 ± 3 days; V7 ± 5 days; V8 ± 5 days. In addition, a 1-day and 3-day (± 1 day) post Visit 2 telephone contact is required to evaluate the subject for any complaints after receiving the study

drug injections. If it is necessary to bring the participant into the clinic for evaluation earlier than required, this may be considered an unscheduled visit, unless the participant has completed the necessary diary pages and the Sponsor or its designee agrees to the window deviation.

7.13 Definition of source data

Source data is defined as all information in original records of clinical findings, observations, or other activities of the clinical trial necessary for the reconstruction and evaluation of the trial. Source data are contained in source documents. Source documents are the original documents, data, and records. Source documents include, but are not limited to hospital records, clinical and office charts, laboratory notes and reports, radiological films and reports, memoranda, participant's quality of life assessments, participants voiding diaries and pharmacy dispensing records.

Study data that should be included in the source documents:

- Participant's identity
- History of the disease
- Medical history, associated diseases (dates of onset)
- History of surgical sterilization, if applicable
- Date and time of administration of the study drug
- Previous and concomitant treatments
- Dates of participation in the study
- A statement on the participant's chart that the informed consent form was signed by the participant
- Dates of study visits / telephone contacts
- Examinations or assessments carried out during the study:
- Laboratory results including cultures
- Vital signs: blood pressure, heart rate, biological exams
- ECGs
- Cystometry readings
- Adverse events (+ follow-up)
- Date of drop-out and reason

Study data that will be considered as raw data:

- Efficacy data entered by diary
- Laboratory test results
- Electronic cystometry results
- ECG tracings
- QoL data

7.14 Access to the randomization code during the study

In case of a Serious Adverse Event, the code must be broken **only** in exceptional circumstances when knowledge of the study medication is essential for treating the participant. If possible, a

contact should be initiated with the Monitoring Team before breaking the code. The data will be reviewed by the DSMB.

For each participant there is a supplied tear off label which should be kept in the participant's source records, affixed to a study treatment label page. This removable panel contains a scratch off laminate which would serve to unblind the treatment if necessary.

7.15 Long-term follow-up

If urine and/or blood samples are still positive for *hSlo* DNA assay at week 24 the participant will be asked to return to the site to give additional urine and/or blood specimens until 2 consecutive specimens are negative.

All participants upon completion or exit from the study will be presented with written instructions on how to contact the sponsor if they experience any serious adverse event that they consider possibly related to study treatment or study participation. All participants receiving bladder injections of *hMaxi-K* will continue to be followed after the completion of all study related procedures (Visit 8 or last study visit) for an additional 18 months. These participants will be contacted at 6 month intervals to evaluate for any safety concerns.

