Participants completed cystometry testing at baseline (prior to dosing) and at Week 4 after dosing, a daily diary at home for 7 days prior to baseline to capture the number of incontinence episodes per week, number of micturitions every 24 hours, volume voided, number of pads used every 24 hours. Micturition diaries were completed daily for 3 days prior to each visit after instillation and quality of life assessments done. Ten participants received the 5000 $\mu\text{g}/90$ ml dose (7 in this group completed the study; 3 discontinued early seeking other treatment for their OAB), 6 participants received the 10000 $\mu\text{g}/90$ ml dose and 5 participants received placebo (all participants completed in the 10000 $\mu\text{g}/90$ ml and placebo groups). There were no serious adverse events reported or a withdrawal for an adverse event. In the 5000 $\mu\text{g}/90$ ml dose, possibly related adverse events reported in one subject each, included urinary tract infection (UTI); AV block Mobitz type II (possibly related; mild severity, 170 days post treatment); fatigue, headache, shaking chills, and insomnia (all possibly related; mild-moderate severity; 13-76 days post treatment). Unrelated events in one subject each (unless otherwise specified) included headache; rash (2 subjects); fractured left (big) toe; infection left (big) toe; worsening of labial adipose lipoma; knee tendonitis; right kidney cyst benign; worsening of depression; worsening of GERD; elevated creatinine; diffuse loss of renal parenchyma; hypertensive renal disease; atypical chest pain; CK elevated (possibly secondary to hypertensive renal disease); CK-MB elevated ((possibly secondary to hypertensive renal disease); diarrhea; vomit, hiatal hernia; bacteriuria, asymptomatic; constipation; fatigue; fall; upper lip abrasion secondary to fall; acne on face; reflux; and UTI (2 subjects). In the 10000 $\mu\text{g}/90$ ml dose group, adverse events were all considered unrelated and included in one subject each, common cold; elevated blood pressure; worsening of urge incontinence; tension headache; low back pain; fall; dysuria; UTI, elevated LFTs; and hepatitis C. In the placebo group heart palpitations were reported in one participant, which were considered possibly related, mild severity, and occurred 6 days post treatment. Unrelated events for placebo that were reported in one participant each included slight irritation at vulva, fractured pelvis (left side) and wrist fracture (left); 4 unrelated UTIs were reported in 2 participants.

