8.1 Participant Withdrawal

While participants are encouraged to complete all study evaluations, they may withdraw from the study at any time and for any reason. Participation is voluntary, and refusal to participate will involve no penalty, or loss of benefits to which the participant is otherwise entitled. The participant will be encouraged to maintain contact with the investigator and report any serious adverse events experienced for the 6 months study period. Follow-up following the study period is described in Section 7.13.

An **evaluable** participant will be any participant who receives at least one dose of test material and has at least one post dose assessment.

Screen failures will include any participant who consented and entered into the screening process appropriately, but subsequently did not meet the entry criteria and was not administered study drug. Participants who fail screening will not be followed for safety or activity of study drug, and no other study procedures will be performed.

Up to a maximum of 3 participants per dose group may be replaced if participants drop out prior to completion of week 4 post study drug.

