9.6 Monitoring of Adverse Events

The investigator will monitor participants for the occurrence of adverse events during the course of the study and record all observed adverse events in the electronic case report form.

All Adverse Events regardless of seriousness or relationship to study drug, including those occurring during the Screening period (where applicable), are to be recorded on the corresponding page(s) in the E-CRF. Whenever possible, symptoms should be grouped as a single syndrome or diagnosis. The Investigator should specify the date of onset, maximal intensity, corrective therapy given, outcome, and his/her opinion as to whether there is a reasonable possibility that the Adverse Event was caused by the study drug.

The investigator must provide the sponsor appropriate information concerning any findings suggesting significant hazards, contraindications, side effects or precautions pertinent to the safety of the study drug. The investigator will instruct participants prior to administration of study drug to report any physical changes or new symptoms that they notice during the course of the study. The investigator must report all serious adverse events (defined above) within 24 hours of their onset or following the investigators awareness of the event to the Sponsor's designee:

[name]
[contact]
[contact]
[contact]

Or

[name]
[contact]
[contact]

The Sponsor or designee will report all serious adverse events to the IRB, FDA, OBA, and NIH according to regulatory requirements. Any adverse event that is not resolved by the end of study (or early termination) visit and considered to be potentially related to study drug, or was the cause for participant withdrawal will be followed as clinically indicated until its resolution, or if non-resolving, until considered stable.

In the case of a Serious Adverse Event the Investigator must immediately:

- SEND (within 1 working day if possible) the signed and dated corresponding page(s) in the SAE Report Form to the Sponsor (as above) or designee. The date of receipt of this form by the Sponsor will be the date used as "Day 1" for expedited reporting to the regulatory agencies as is required.
- ATTACH the photocopy of all examinations carried out and the dates on which these examinations were performed. For laboratory results, include the laboratory normal ranges.
- All additional data or corrections are to be reported on a follow-up SAE form.

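### For women who leave before Week 24, Protocol 7.15 and 8.1 set different serious-event reporting rules, so an event the participant does not link to treatment may surface late on hMaxi-K or never on placebo

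*Protocol*

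**What the plan says.** - **Protocol 7.15, exit instruction.** "All participants upon completion or exit from the study will be presented with written instructions on how to contact the sponsor" about "any serious adverse event that they consider possibly related to study treatment or study participation". The same section adds contact every 6 months for 18 months after Visit 8 or the last study visit, open to any safety problem, but for hMaxi-K recipients only. Protocol 3.2 also limits this follow-up to active treatment.
- **Protocol 8.1, withdrawal.** The participant is "encouraged to maintain contact with the investigator and report any serious adverse events experienced for the 6 months study period". For later follow-up it adds: "Follow-up following the study period is described in Section 7.13". In the body of the protocol, 7.13 defines source data; long-term follow-up is 7.15. Protocol 3.2 points to 7.12, which is the visit schedule and windows.
- **Protocol 8.2.** A participant who discontinues is to be contacted about her reasons and any adverse events, and the Visit 8 procedures should be completed.
- **Protocol 9.4.** Relatedness is the principal investigator's estimate.
- **SAP 10.1.** Adverse events in long-term follow-up go to separate listings, outside the main analyses.

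**The concern.** The primary objective is the occurrence of adverse events and their relationship to hMaxi-K compared with placebo. That comparison needs serious events to reach the investigator by the same route in both arms for the full 24 weeks, before anyone has judged their cause.

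For an early leaver, the sheet she takes home asks for serious events she herself thinks may be related. An event she does not connect with a bladder injection need not be reported under that sheet, so it may never reach the person who is meant to assess causality. The later unfiltered contact that could recover it exists in one arm only. A late report from the first cohort could also arrive after the escalation review in Protocol 5.2.2, which takes place 4 weeks after the last participant in the cohort is dosed.

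**Working it through.** The plan states no figure to reproduce. The check is a comparison of texts with simple arithmetic.

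**1. The two rules side by side**

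| | Protocol 7.15 (exit sheet) | Protocol 8.1 (withdrawal) |
|---|---|---|
| Who | everyone, at completion or exit | participants who withdraw |
| Which events | serious, and thought possibly related by the participant | any serious event |
| Reported to | the sponsor | the investigator |
| Period | from completion or exit, no end stated | the 6-month study period |

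**2. Where they overlap**

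- Completer: 8.1 ends with the study period and 7.15 begins at Visit 8 (Week 24). There is no overlap and no conflict.
- Leaver at Week *w*: both apply for 24 − *w* weeks. For *w* = 4 that is 20 weeks; for *w* = 12 it is 12 weeks.

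**3. When an unreported event would next be asked about**

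- hMaxi-K: 18 / 6 = 3 scheduled contacts, with a longest gap of 6 months. Protocol 7.15 gives the interval but not the date of the first contact. Assume it falls 6 months (about 26 weeks) after the last study visit. A leaver at Week *w* is then first asked at about Week *w* + 26, which is Week 30 for *w* = 4. Since *w* + 26 exceeds 24 for every *w* ≥ 0, no such contact falls inside the 24-week window.
- Placebo: no scheduled contact after exit.
- By plan this splits 2 × 6 = 12 hMaxi-K recipients from 2 × 3 = 6 placebo recipients.

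**4. What the analysis would do with the event**

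- SAP 6 keeps every dosed participant in the Safety Population, and SAP 7.5 imputes no adverse-event data. A leaver whose serious event is never reported stays in the denominator and counts as event-free.
- Protocol 7.15 starts long-term follow-up at Visit 8 or the last study visit. A Week 10 event in a Week 4 leaver therefore began after her long-term follow-up started, yet within 24 weeks of dosing. SAP 10.1 does not say whether it belongs in the main tables or the separate listing.

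**5. Size of one event**

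- One dose group or pooled placebo: 1 / 6 = 16.7 percentage points.
- Combined hMaxi-K: 1 / 12 = 8.3 percentage points.
- Early leaving in the earlier OAB trial (Protocol 1.4.2): 3 of 10 on 5000 µg, 0 of 6 on 10000 µg and 0 of 5 on placebo, so 3 / 21 = 14.3% overall. That trial reported no serious events.

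**The case against.** The strongest reply is that the two sections can both be followed. Protocol 7.15 does not say that other serious events should be withheld; a reader may infer that only related events are wanted, but the word is not there. A leaver can call the sponsor under 7.15 and still tell the investigator about everything under 8.1. Protocol 9.6 also has the investigator instruct participants, before dosing, to report any new symptoms during the study. Protocol 8.2 adds an unfiltered contact at discontinuation, and the 6-monthly contacts are unfiltered too. Most of the time governed by 7.15 lies after Week 24, where SAP 10.1 keeps events out of the main tables anyway.

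Much of this stands. The safeguards are real, and for hMaxi-K recipients who stay reachable the expected harm is delay. But the 8.2 contact happens once, around discontinuation, and does not cover the weeks that follow. The written instruction specified for the participant at exit carries the narrower rule, and 8.1's pointer to later follow-up leads to the wrong section. None of the safeguards gives a placebo leaver a scheduled contact after she has gone.

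A reader might also infer that 7.15 contradicts 9.6, which requires recording of "All Adverse Events regardless of seriousness or relationship to study drug". It does not. Protocol 9.6 sets the investigator's duty: "The investigator will monitor participants for the occurrence of adverse events during the course of the study". Its 24-hour clock runs from onset or the investigator's awareness, whatever the relationship. The 7.15 wording can reduce what the investigator hears, but it does not change that duty.

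**Conclusion.** The point holds for early leavers. Protocol 7.15 and 8.1 give them different rules on scope and recipient for the same weeks, and the possible under-capture differs by arm: up to about 6 months late on hMaxi-K, possibly never on placebo.

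It matters only if a participant leaves before Week 24, has a serious event after the 8.2 contact, does not link it to treatment, and follows the exit sheet rather than 8.1. The 6-month figure assumes that contacts occur on schedule and that she can be reached. No document says what share of serious events participants would attribute to the study, so the number missed cannot be estimated. The firm figures are the contact gap and the weight of one event in a group of 6. Loss is therefore a risk, not a certain outcome.

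One further inference should be resisted. The earlier OAB trial recorded "AV block Mobitz type II (possibly related; mild severity, 170 days post treatment", and a reader might take this as proof that such a filter fails. The event was mild, that trial had no serious events, and nothing says it used a similar exit instruction. In the present trial an ECG is already scheduled at Visit 8 and is due at early discontinuation. The case does not bear on the reporting of serious events.

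The change is worth making because it is cheap and improves capture inside the primary safety window.

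**What to change.** 1. **Protocol 7.15 and the exit sheet:** ask participants to report any serious adverse event, whatever they think caused it, and leave causality to the investigator under 9.4.
2. **Protocol 7.15 and 8.1:** give early leavers one rule through Week 24, with the same scope and a named recipient.
3. **Cross-references:** change 7.13 in 8.1 to 7.15, and correct the pointer to 7.12 in 3.2 at the same time.
4. **SAP 10.1:** state that a serious event with onset by Week 24 counts in the main serious TEAE summary even if it is learned of at a later contact, and keep the separate listing for events with later onset.

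The cost is a wording change in two documents and the exit sheet, plus a few more clearly unrelated reports to process among at most 18 planned participants. No visit, test or sample-size change is needed. Rewording does not give placebo leavers a scheduled contact; it removes the filter from what they are asked to report.
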